Islam 1996[31]	Bangladesh	Children 1-23 months hospitalized with diarrhea	7.5% within 3 months	Age < 6 months, malnutrition, not breastfeeding, lack of immunization

Table 1b. Hospital re-admission in low-resource settings

Study	Location	Population	Re-admission
Moisi 2011[7]	Kilifi, Kenya	Children <15 years discharged from hospital	17.7% over follow-up period (avg 2.8 years)
Snow 2000[9]	Kilifi, Kenya	Children followed in surveillance cohort with a hospital admission	40.9% over total follow-up period (9% within 3 months)
Veirum 2007[8]	Guinea-Bissau	Children admitted to hospital	20.1% re-admitted over 1 year follow-up
Phiri 2008[29]	Malawi	Children 6-60 months hospitalized with severe anemia	9.4% within 18 months (17.2% among anemia cases)

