Illness following discharge from hospital is often the result of preventable and treatable infectious diseases. Infectious morbidity and subsequent mortality following hospitalization may be due to incompletely or inadequately treated infection, nosocomial infections that present following discharge, or new infections resulting from repeated exposure once the child returns to the community. In a large study of 1148 children admitted to hospital in Kenya, more than a quarter (27%) were readmitted following discharge, with over half of those admission occurring within 6 months. Of these admissions, almost half (47.8%) were due to malaria, 26.4% due to acute respiratory disease, and 8.2% due to gastroenteritis.[9] In Western Kenya, over three quarters of all early deaths following discharge occurred among children who were originally hospitalized with malaria or bacteremia, while in Bangladesh, all children who died following hospitalization for diarrhea had persistent symptoms of gastroenteritis preceding death.[17, 23, 24] Nosocomial infections also contribute significantly to recurrent illness following hospitalization and are often unrecognized at discharge. In Kenya, nosocomial bacteremia was documented in almost 6/1000 admissions, with a mortality rate that was more than twice that seen for community-acquired bacteremia (53% vs. 24%).[32] Finally, children discharged from hospital usually return to the communities and exposures from which they originally came. As a result, repeated exposure to community-acquired infections (including malaria, acute respiratory infection, and diarrhea) may contribute to post-hospitalization morbidity and mortality. For example, in Kenya, diarrheal disease and malaria are the most significant diseases contributing to mortality within three months of discharge.[9, 23] Targeted antimicrobial interventions to cover residual infection, reduce carriage of pathogens, and provide prophylaxis against common exposures may significantly impact infectious morbidity and mortality in the post-discharge period.

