calculated for the primary endpoint of time to death or hospital re-admission within the 6 month post-discharge period, assuming an alpha level of 0.05, power of 0.80, and a ratio of treatment to placebo random assignment of 1:1. In sub-Saharan Africa, it is estimated that 2-15% of children aged less than 5 years died within 6 months of hospital discharge 15.5% of children who survived discharge from the district hospital re-admitted with the same diagnosis within 6-months[7, 9, 25] Assuming

an additional 5-10% of children are re-admitted for other conditions, we expect that re-hospitalizations will occur in 20.5 to 30.5% of children enrolled in the study. Combined with our expected fatality rate (2-15%), we expect the cumulative incidence of the combined endpoint to range from 22.5 to 45.5%. [25] Based on a previous trial of mass drug administration of a single dose of azithromycin in which a single dose of the antibiotic was associated with a 49% reduction in risk of death, we calculated sample sizes using estimates of reduction in risk ranging from 30-50% with the cumulative incidence range of 22.5 to 45.5%, and found the sample size required ranged from 90 to 550 children per treatment arm.[10] Using the most conservative estimates of a hazard ratio of 0.70 and 22.5% prevalence of re-admission/death, we need to enroll 1100 children in the study (550 per arm) to achieve adequate power. We will recruit an additional 300 children ($\approx 20\%$) to account for possible loss to follow-up, resulting in a total planned enrollment of 1400 children, or 700 per treatment group. When considering mortality alone, and estimated mortality ranges of 2-15%, we will have $>80\%$ power to detect hazard ratios ≤ 0.5 for mortality rates of $\geq 8\%$ and hazard ratios ≤ 0.6 for mortality rates $\geq 11\%$ (Figure 6). Although the ability to determine differences in mortality between arms will require either a high mortality rate or a large measure of effect, in Kenya, re-hospitalization is associated with as much as a 23.6-fold increased risk of death, indicating that this outcome is itself a severe outcome and an intermediate marker of death.[7]

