Prevalence of Shigella , Salmonella , Campylobacter , Cryptosporidium , Giardia @ enrollment, day 90, and day 180	Visits that occur within 30-days on either side of 90-days (M3) and 180-days (M6) visits will be included. Therefore, visits occurring outside of 60-120 days post-enrollment for M3 and outside of 150-210 days post enrollment for M6 will be excluded from the primary analysis but included in sensitivity analyses.
Streptococcus pneumoniae (S. pneumoniae) prevalence @ enrollment, day 90, and day 180	Visits that occur within 30-days on either side of 90-days (M3) and 180-days (M6) visits will be included. Therefore, visits occurring outside of 60-120 days post-enrollment for M3 and outside of 150-210 days post enrollment for M6 will be excluded from the primary analysis but included in sensitivity analyses.
Prevalence of resistance to azithromycin in E.coli and S. pneumoniae and prevalence of ESBL-producing E.coli @ enrollment, day 90, and day 180	Visits that occur within 30-days on either side of 90-days (M3) and 180-days (M6) visits will be included. Therefore, visits occurring outside of 60-120 days post-enrollment for M3 and outside of 150-210 days post enrollment for M6 will be excluded from the primary analysis but included in sensitivity analyses.

SECTION 4. STATISTICAL PRINCIPLES

Confidence Intervals and P values

Level of statistical significance

All statistical tests will be 2-sided using a 5% significance level (alpha of 0.05). For the primary aim (aim 1), an alpha of 0.045 will be used for hypothesis tests that were part of the interim analysis to account for alpha spending.

Type I errors

We will not adjust the alpha for multiple testing in the primary aim. Instead we will clearly state primary and secondary analyses and interpret secondary analyses as hypothesis-generating rather than confirmatory. All secondary aims will be adjusted for multiple comparisons using the Benjamini and Hochberg method using a false discovery proportion of 0.05.

Confidence intervals to be reported

For the primary analysis of Aim 1, two-sided 95.5% confidence intervals will be used to account for the 0.045 alpha spent at the interim analysis. All other analyses will utilize two-sided 95% confidence intervals.

Adherence and Protocol Deviations

Definition of adherence to intervention and how this is assessed including extent of exposure

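### The planning event rate contains a sum error at its top end and allows no overlap between deaths and readmissions, so 22.5% is not the floor and the stated 80% power has almost no slack

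*Protocol*

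**What the plan says.** Protocol, Sample Size, Aim 1, sizes the trial on the "primary endpoint of time to death or hospital re-admission within the 6 month post-discharge period". The error rates are alpha 0.05 and 80% power, with equal arms. It takes 15.5% readmission with the same diagnosis within 6 months and assumes "an additional 5-10% of children are re-admitted for other conditions". From these it states "we expect that re-hospitalizations will occur in 20.5 to 30.5% of children enrolled in the study". It then adds expected mortality of 2-15% and gives a composite range of 22.5-45.5%. Over hazard ratios from 0.50 to 0.70 this yields 90 to 550 children per arm.

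The sentence that fixes the sample size opens "Using the most conservative estimates of a hazard ratio of 0.70 and 22.5% prevalence of re-admission/death" and arrives at 550 per arm. A further 300 children for loss to follow-up (about 20%) bring the total to 1,400. SAP Section 3 (Sample size) carries 22.5% forward and refers to the protocol for details. SAP Sections 3 and 4 set alpha at 0.045 for the final primary test.

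**The concern.** The upper readmission figure does not follow from the two inputs printed beside it, and the error passes into the composite range and the favourable end of the sample size range.

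The construction of the composite is also unsound in kind. A child who is readmitted and later dies contributes one first event, so adding the two percentages is right only if no child has both. The same paragraph says readmission carries up to a 23.6-fold higher risk of death, which makes zero overlap implausible. Zero overlap gives the highest composite rate the inputs allow, so a rate built that way should not be called most conservative without qualification.

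What is at stake is the stated 80% power for the primary endpoint. It depends directly on the event rate, and the margin above 80% turns out to be about one percentage point.

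**Working it through.** **Inputs.** From Protocol, Sample Size, Aim 1: 15.5% same-diagnosis readmission, a 5-10% add-on, 2-15% deaths, hazard ratio 0.70, power 0.80, 1:1 allocation, 1,400 enrolled, about 20% loss. From SAP Section 4: "All statistical tests will be 2-sided using a 5% significance level (alpha of 0.05", with 0.045 for the final primary test. Evaluable children: 1,400 × 0.80 = 1,120.

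**1. The plan's own figure.** Schoenfeld events = 4 × (1.960 + 0.842)² / (ln 0.70)² = 4 × 7.849 / 0.1272 = 246.8, so 247. Then 247 / 0.225 = 1,098, or 549 per arm. The stated 550 per arm reproduces, with 22.5% read as the event probability over both arms together. The SAP's 157 interim events fit the same reading: 1,400 × 0.225 / 2 = 157.5.

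**2. The sum.** 15.5 + 5 = 20.5 and 15.5 + 10 = 25.5. The printed 30.5 would need an add-on of 15. On the protocol's own addition the composite is 20.5 + 2 = 22.5% to 25.5 + 15 = 40.5%. The lower end, and with it 1,100 and 1,400, is unchanged.

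**3. The low end of 90 to 550 per arm.** At hazard ratio 0.50 the events needed are 65.3. No formula is printed, so two readings are shown:
- 45.5% as the placebo rate with proportional hazards: treated rate 1 − 0.545^0.5 = 26.2%; 65.3 / (0.455 + 0.262) = about 91 per arm. At 40.5% (treated 22.9%) it is about 103.
- 45.5% as the rate over both arms: 65.3 / 0.455 / 2 = about 72 per arm. At 40.5% it is about 81.

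Only the first comes near the printed 90, whereas the printed 550 matches the second. The top end of the rate range changes the result on either reading.

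**4. Overlap.** Independence: a + b − ab.

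| Assumption | Low end (20.5%, 2%) | High end (25.5%, 15%) |
|---|---|---|
| No overlap | 22.5% | 40.5% |
| Independent | 20.5 + 2 − 0.41 = 22.1% | 25.5 + 15 − 3.8 = 36.7% |
| Every death preceded by readmission | 20.5% | 25.5% |

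**5. Power.** Power = Φ(0.3567 × √(1,120 × rate) / 2 − z), with z = 1.960 at alpha 0.05 and 2.005 at 0.045.

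| Composite rate | Events | Power, 0.05 | Power, 0.045 |
|---|---|---|---|
| 22.5% | 252 | 80.8% | 79.6% |
| 22.1% | 247 | 80.1% | 78.8% |
| 20.5% | 230 | 77.1% | 75.7% |
| 19.5% | 218 | 75.0% | 73.6% |
| 17.5% | 196 | 70.4% | 68.9% |
| 15.5% | 174 | 65.2% | 63.5% |

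At alpha 0.045, 80% power needs 4 × (2.005 + 0.842)² / 0.1272 = about 255 events.

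**6. What the cited cohorts say.**
- One Kilifi cohort in Tables 1a and 1b had 9% readmitted and 1.4% dead at 3 months. Summed without overlap this is 10.4%. If the hazard does not rise, the 6-month figure is at most 1 − 0.896² = 19.7%.
- In Guinea-Bissau, "20.1% re-admitted over 1 year follow-up". With 7.5% deaths the sum is 27.6% at 12 months. It reaches 22.5% at 6 months only if about 82% of the year's events fall in the first half (22.5 / 27.6).
- Pointing the other way, Table 1a gives 15% deaths within 8 weeks in Western Kenya, with no readmission figure.
- The documents disagree on one source. The Background text says "more than a quarter (27%) were readmitted following discharge, with over half of those admission occurring within 6 months", while Table 1b gives 40.9% over total follow-up for the same cited study.

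**The case against.** The strongest reply is that none of this changes the trial. The sum error lies in figures that were not used for sizing, and the slip may be in the add-on: 5-15% would give 30.5%. Both points stand, and the fix allows for the second.

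On overlap, full overlap is an extreme. The Background says many children die before reaching care, and the protocol plans household verbal autopsies. Under independence the loss is 0.4 points and power stays at 80% at alpha 0.05. That also stands: 20.5% is a bound, not an expectation.

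In context, 'most conservative' picks the least favourable corner of the grid just stated. This is fair as description, but the grid itself was built on the most favourable overlap assumption.

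A reader might go further and infer that 22.5% is near the top of what the protocol's own data allow. The documents do not support that. Halving 27% gives 13.5% all-cause readmission, which is below the protocol's 15.5% for same-diagnosis readmission alone. It is also a floor (the text says over half), and it leaves out deaths. Half of 40.9% would be about 20.5% for the same study. The 15% mortality in Western Kenya points upward. The cohort with 17.7% readmission over 2.8 years includes children up to 15 years, whereas the trial stops at 59 months.

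Finally, Potential Challenges and Limitations says a changed sample size could be considered if events are fewer than predicted. This softens the point. It gives no trigger, however, and the SAP contains no re-estimation rule.

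**Conclusion.** The point holds in limited form. The readmission and composite upper ends, 30.5% and 45.5%, do not follow from the stated inputs, and the low end of the sample size range inherits the error. The design figures of 22.5%, 1,100 and 1,400 are not affected by the sum.

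The missing overlap does reach the design rate. It falls to between 22.1% and 20.5%, so 22.5% is the bottom of the range only if no child is both readmitted and dies. Power falls from 81% to between 80% and 77% at alpha 0.05, and from 79.6% to between 79% and 76% at the final alpha of 0.045. The loss is small, but there was almost no margin to absorb it.

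The cohort figures justify showing lower rates as sensitivity values and nothing stronger. Nor is there ground to say that a null result would be misread: confidence intervals for the primary result are already planned.

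These figures assume proportional hazards, no information from the 20% lost, and 22.5% as the rate over both arms. They treat the final test alone, without the interim look. SAP Section 3 labels 22.5% the placebo rate. On that reading power at 22.5% and alpha 0.05 is already about 75%, which is a separate matter to reconcile.

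**What to change.** In Protocol, Sample Size, Aim 1:
- Correct the readmission range to 20.5-25.5%, or correct the 5-10% add-on if that is the slip.
- Restate the composite range with one overlap assumption applied at both ends: 22.5-40.5% (none), 22.1-36.7% (independent) or 20.5-25.5% (full). If the add-on is the slip, the upper ends become 45.5%, 40.9% and 30.5%.
- Recompute the low end of the 90 to 550 range to match, and name the formula.
- Describe 22.5% as the lowest value of the assumed range under no overlap, in place of an unqualified 'most conservative'.

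In the protocol and SAP Section 3, print power at the final alpha of 0.045 with 1,120 evaluable children for composite rates of 15.5%, 17.5%, 19.5%, 20.5% and 22.5% (63.5%, 68.9%, 73.6%, 75.7% and 79.6%). State that about 255 events are needed for 80% power.

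The cost is text and a less favourable stated power. No extra enrolment and no change to the analysis are needed.

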Exclusion criteria:	Contraindication to azithromycin use (the use of another macrolide antibiotic [i.e. erythromycin or clarithromycin]); known macrolide allergy; current use of Lopinavir; residence in an orphanage or children's home; previous participation in the Toto Bora Trial; sibling enrolled in Toto Bora Trial on same day.
Target enrollment:	1400 (700/arm)
Intervention	5-day course of azithromycin or placebo
Duration of follow-up:	6 months (enrollment, 90 days, and 6 months) (Figure 3)
Sampling framework:	All children hospitalized for non-traumatic cause, and subsequently discharged, from study sites during recruitment period

Eligibility

Children age 1 to 59 months old who weigh at least 2 kg and have been hospitalized and subsequently discharged from hospitals in Kisii or Homa Bay County for non-traumatic conditions will be eligible for the RCT (Aim 1). We will exclude children in whom azithromycin is contraindicated, such as those children currently taking another macrolide antibiotic, such as erythromycin or clarithromycin, those with a known macrolide allergy, and those who do not plan to remain in the study site catchment area for at least 6 months. A random subset of 300 children (150 from each arm) will be selected into the **Enteric Function Cohort**

Figure 3. Proposed study design

(Aims 2 and 3). We will also enroll a primary caregiver of each the 300 children enrolled in the **Enteric Function Cohort** in the **Contact Cohort** (Aim 2b). These caregivers must be at least 18 years of age or classified as an emancipated minor by Kenyan law, plan to remain in study site catchment area for at least 6

months and be willing/able to provide a stool and nasopharyngeal sample at enrollment, 90 days and 6 months of follow-up if randomized to the **Contact Cohort**.

Sample Size

Aim 1. To compare rates of re-hospitalization and mortality in the 6 months following hospital discharge among children receiving 5-day azithromycin vs. placebo. The total sample size required was

[figure not shown]

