Aim 2a. To evaluate possible mechanism(s) by which azithromycin may affect morbidity and mortality, by comparing reasons for re-hospitalization, prevalence of pathogen carriage, and markers of enteric dysfunction between the randomization arms. We calculated the minimum detectable association between treatment arm and cause-specific re-hospitalizations (hospitalization due to diarrhea, acute respiratory infection, malnutrition, or malaria vs. any other) among enrolled children, assuming an alpha level of 0.05, power of 0.80, and a ratio of treatment to placebo of 1:1. Based on data from Kenya, re-hospitalization rates due to specific causes ranged from approximately 0.5% to 5.7% in the 6 month post-discharge period, with the lowest rate reported for gastroenteritis and the highest for malaria.[9] By not conditioning on the child having the same diagnosis at initial hospitalization, we expect the cumulative incidence of cause-specific re-hospitalizations to range from 2.5% to 10%. With this range of outcome rates, we will be able to detect hazard ratios of 0.48 to 0.70 for the effect of azithromycin on specific severe morbidities.

Among the 1400 children in whom nasopharyngeal swabs and stool samples are cultured, we expect 56% of children in the placebo group to have *S. pneumoniae* identified based on data from Kenya, providing $\geq 80\%$ power to detect a prevalence ratio of 0.85 (or 1.15) between the two treatment arms at each time point.[51-53] Because there is a strong link between carriage of *S. Pneumoniae* and development of associated disease, and because empiric azithromycin has been shown to prevent reduce clinical pneumonia by as much as 75% in an outbreak setting, we believe that our ability to detect a 15% reduction in risk is appropriately sensitive.[54, 55] Based on prevalence of *Salmonella* spp., *Shigella* spp., *Campylobacter* spp., or diarrheagenic *E. coli* (ETEC, EHEC, EPEC, and EAEC) among asymptomatic children in Western Kenya, we expect 20% of children in the placebo group to have a bacterial pathogen isolated at each time point, resulting in $\geq 80\%$ power to detect differences in enteric pathogen prevalence of 0.68 (1.36) at each time point.[48]

Figure 6. Power and detectable hazard ratios given a range of mortality rates

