To determine the number of children needed to evaluate the effect of azithromycin on biomarkers of enteric inflammation children in the **Enteric Function Cohort**, we assumed an alpha level of 0.05, power of 0.80, and a ratio of treatment to placebo of 1:1. For the outcome of enteric inflammation, and assuming a clinically relevant unit mean difference of 2.8mg/L, and a standard deviation of 7.8mg/L, 250 individuals would need to be enrolled to achieve adequate power to detect associations between the intervention groups.[56, 57] We will enroll 300 children (150 per arm) in this cohort in order to account for 20% potential loss to follow-up.

*Aim 2b. To determine whether empiric administration of azithromycin at hospital discharge increases risk of antimicrobial resistance in commensal *Escherichia coli* (*E. coli*) and pneumococcal isolates from treated children and their household contacts.* We will select a random selection of 400 *E. coli* and 400 *S. pneumoniae* isolates (200 per arm) for β -lactam and macrolide resistance testing. We will also store all *S. pneumoniae*, *E. coli* isolates and other isolated bacteria from stool for potential future testing in the event that resistance prevalence is lower than expected. As shown in Table 7, we will have > 80% power to detect prevalence ratios > 1.1, with an ability to detect the smallest effect sizes when the prevalence of resistance in the placebo group is highest.

While we expect that all 300 adults in the Contact Cohort will have *E. coli* isolated and available for resistance testing, ranges for adult *S. pneumoniae* carriage in Sub-Saharan Africa range from 5-55%. Therefore, we expect 15 to 165 *S. pneumoniae* isolates to be available for resistance testing.[51, 58, 59] Assuming an alpha of .05, a 1:1 ratio of testable isolates, and a prevalence of resistance of 50% in the placebo arm, we will have 80% power to detect a 1.4-fold higher prevalence to 1.9-fold higher resistance prevalence in the contacts of azithromycin-treated children.

Aim 3. To identify correlates and intermediate markers of post-discharge mortality and hospital readmission among hospitalized children.

Conservatively estimating a 20% loss-to-follow-up rate in the RCT and a cumulative incidence of death or re-hospitalization of 22.5%, we will have >80% power to detect hazard ratios ≥ 1.3 between correlates and the outcome with exposure prevalence of $\geq 20\%$ or more and hazard ratios ≥ 1.5 for exposure prevalence <20%.

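### Protocol, Aim 2a: at the stated rates and enrollment, power for cause-specific re-hospitalization hazard ratios of 0.48 to 0.70 is roughly 40–58%, not 80%

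*Protocol*

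**What the plan says.** The claim is in the Protocol, Sample Size, Aim 2a. The inputs are "assuming an alpha level of 0.05, power of 0.80, and a ratio of treatment to placebo of 1:1", and the expected rate is given as "we expect the cumulative incidence of cause-specific re-hospitalizations to range from 2.5% to 10" percent. From these the protocol concludes that "we will be able to detect hazard ratios of 0.48 to 0.70 for the effect of azithromycin on specific severe morbidities". It does not say whether the rates are for the placebo arm or for both arms together, whether the test is one- or two-sided, or how many children the calculation counts.

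The missing inputs are found elsewhere:

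- **Sidedness.** SAP, Level of statistical significance: "All statistical tests will be 2-sided using a 5% significance level (alpha of 0.05").
- **Size.** Protocol, Sample Size, Aim 1: "resulting in a total planned enrollment of 1400 children, or 700 per treatment group".
- **Loss.** Protocol, Sample Size, Aim 3: "Conservatively estimating a 20% loss-to-follow-up rate in the RCT".
- **Follow-up.** Six months (Protocol, Table 4).

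Aim 1 gives a benchmark for the method. For a hazard ratio of 0.70 and a 22.5% event rate, "we need to enroll 1100 children in the study (550 per arm) to achieve adequate power".

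**The concern.** Aim 1 needs 1,100 children and a 22.5% rate to detect a hazard ratio of 0.70. Aim 2a claims the same hazard ratio at a rate of at most 10%, less than half as high, in a trial of at most 1,400. The same section says that, for mortality, more than 80% power is available for hazard ratios of 0.6 or below at rates of 11% or above. That is a stronger effect at a higher rate than the 0.70 at 10% claimed for cause-specific admissions. For one trial, one alpha and one power, these statements cannot all hold.

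What is at stake is how non-significant results are read. The SAP analyses diarrhea, pneumonia, malnutrition and malaria separately and refers to the protocol for sample-size details. A reader relying on the printed range could take a null result for one diagnosis as evidence against a 30% reduction in hazard, although the trial would miss a reduction of that size about half the time even at the highest assumed rate.

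**Working it through.** **Formula.** Schoenfeld, 1:1 allocation, two-sided alpha 0.05, power 0.80:

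- events needed = 4 × (1.960 + 0.842)² / (ln HR)² = 31.40 / (ln HR)²
- power with d events = Φ(√d × |ln HR| / 2 − 1.960)
- detectable HR = exp(−√(31.40 / d))

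**1. Reproduce the protocol's other figures.**

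- Aim 1: HR 0.70 needs 31.40 / 0.1272 = 247 events. Dividing by 0.225 gives about 1,097 children, against 1,100 in the protocol. The match requires 22.5% to be the rate across both arms; read as a placebo rate, 1,100 children give 74% power.
- Mortality: HR 0.6 needs 120 events. With 1,400 × 0.80 = 1,120 children at 11% there are 123, giving 81% power, as claimed.

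**2. Events needed for the Aim 2a range.**

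- HR 0.48: 31.40 / 0.5387 = 58
- HR 0.70: 247

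The pairing most favorable to the plan is used: the strongest effect with the lowest rate. HR 0.70 at 2.5% would have only 15–18% power on the pooled reading.

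**3. Events available and power, rates pooled over both arms.**

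| Children | Rate | Events | HR | Power | Events needed ÷ available | HR detectable at 80% |
|---|---|---|---|---|---|---|
| 1,400 | 2.5% | 35 | 0.48 | 58% | 1.67 | 0.39 |
| 1,400 | 10% | 140 | 0.70 | 56% | 1.76 | 0.62 |
| 1,120 | 2.5% | 28 | 0.48 | 49% | 2.08 | 0.35 |
| 1,120 | 10% | 112 | 0.70 | 47% | 2.20 | 0.59 |

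**4. The same, with the rates read as placebo-arm rates.** Events = n per arm × [p + 1 − (1 − p)^HR].

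| Children | Rate | Events | HR | Power | HR detectable at 80% |
|---|---|---|---|---|---|
| 1,400 | 2.5% | 26.0 | 0.48 | 46% | 0.31 |
| 1,400 | 10% | 119.8 | 0.70 | 50% | 0.59 |
| 1,120 | 2.5% | 20.8 | 0.48 | 39% | 0.26 |
| 1,120 | 10% | 95.8 | 0.70 | 42% | 0.55 |

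**5. What the printed range would need.** On the pooled reading, 58.3 / 0.025 = about 2,330 children for HR 0.48 and 246.8 / 0.10 = about 2,470 for HR 0.70, all followed. Alternatively, with 1,400 children, rates of about 4.2% and 17.6%.

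**6. Other methods.** For the same pairs and 550 to 700 children per arm, Freedman's formula, a pooled two-proportion test and a one-sided 5% test were also tried. None reaches 80%. The highest is 70%: one-sided Schoenfeld, pooled rate, no loss.

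**The case against.** The shortfall in the arithmetic is hard to dispute. The objections concern its weight and its edges.

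- **It is a secondary aim.** The 1,400 was sized on death or re-hospitalization only, and no stopping boundary or decision rule uses 0.48 to 0.70. This stands. A reader might infer that the trial is too small for its primary question; the documents do not support that, because the Aim 1 figure reproduces. Nor do they rank cause-specific admission above pathogen carriage or enteric markers as a test of mechanism.
- **The SAP already limits over-reading.** It calls secondary analyses hypothesis-generating, applies Benjamini–Hochberg to the secondary aims, and reports 95% intervals for everything except the primary analysis. This reduces the harm but leaves the figure uncorrected. The multiplicity adjustment is not in the calculation and can only lower power.
- **Loss is overstated.** Under the SAP's Missing Data section, children without outcome data are censored at their last visit and keep their person-time, and the protocol adds weekly monitoring of admissions. The 20% rows are therefore a worst case, but the no-loss rows also fall short.
- **The planned model counts repeat admissions.** Andersen–Gill could add events. On the pooled reading, 67–76% more would be needed with no loss and 108–120% more with loss. The documents give no recurrence rate, and the claim is stated on cumulative incidence. A rescue cannot be excluded, but nothing in the plan supports one.
- **The combined diagnosis may do better.** The SAP also plans an endpoint of any of the four diagnoses, with no rate given. If 15% to 20.5% is assumed (20.5% being the lower end expected for all re-hospitalization), the detectable hazard ratio is 0.68–0.72 with 1,400 children and 0.65–0.69 with 1,120. It would be wrong to infer that no cause-related analysis can detect anything weaker than about 0.6.

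A reader might also guess that the 1,120 children left after loss were counted per arm. That gives 0.473 and 0.688, not the printed values, and Aim 1 counts correctly in total. The documents do not show how the error arose.

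**Conclusion.** The Aim 2a statement is wrong as written. At the printed hazard ratios, power is 56–58% with complete follow-up and 47–49% if 20% of children contribute nothing (pooled rates), or 46–50% and 39–42% (placebo-arm rates), against the 80% claimed.

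This rests on a two-sided 5% test, first events only, proportional hazards and no multiplicity adjustment. The documents do not settle which rate convention applies: the pooled reading matches Aim 1, while the carriage calculations that follow in Aim 2a use placebo-group rates. The conclusion is the same either way.

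It is a reporting error in a secondary aim. It affects how null single-diagnosis results should be read and does not affect the primary sample size or analysis.

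**What to change.** Replace the Aim 2a sentence in the protocol with:

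> Assuming 2.5% to 10% is the cumulative incidence across both arms, two-sided alpha 0.05, first events only and no multiplicity adjustment, we have 80% power to detect hazard ratios of 0.39 (2.5%) to 0.62 (10%) with complete follow-up and 0.35 to 0.59 with 20% loss; if these are placebo-arm rates, 0.31 to 0.59 and 0.26 to 0.55.

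If the sponsor states which convention was meant, the other half can be dropped. If a recurrence rate for the Andersen–Gill model can be justified, it should be stated and the figures recomputed.

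Any matching SAP sentence should be limited to the single-diagnosis endpoints at these rates, leaving out the combined diagnosis. It should say that a non-significant result there does not rule out hazard ratios of about 0.6 to 1.

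The cost is one sentence in the protocol and at most one in the SAP. Enrollment, procedures and the primary analysis do not change; the stated sensitivity becomes less favorable.
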